3.7. Data Handling Conventions and Transformations

Age (in years) on the registry start date (i.e., Day 1 Visit of the registry collected from the demographic eCRF) and sex at birth will be used for analyses and presentation in listings. If age at Day 1 is not available for a participant, then age derived based on date of birth and the Day 1 visit date will be used instead. For screen failures, the date when the first informed consent was signed will be used for the age derivation.

The following conventions will be used for the imputation of date of birth when it is partially missing or not collected:

- If only month and year of birth is collected, then “15” will be imputed as the day of birth
- If only year of birth is collected, then “01 July” will be imputed as the day and month of birth
- If year of birth is missing, then date of birth will not be imputed.

For some countries, only birth year is collected on the eCRF. In those cases, “01 July” will be used for the unknown birth date and month for the purpose of age calculation, unless age is captured on the eCRF.

When calculating duration of follow-up, time to events such as HCC occurrence and death, partial dates will be imputed as 01 if only day is missing, as 01 January if day and month are missing; and if the imputed death date was before the last available visit date for a participant, the partial death date will be re-imputed as the same of the last available visit date.

For an HCC event that is reported in multiple visits, the earliest diagnosis date is used as the first HCC event occurrence date.

For an endoscopy/liver imaging test conducted on one day but repeatedly reported in multiple visits, it will be assigned to the correct analysis window as in Section 3.8.2. The milder record will be selected for baseline if there are different reported test results (e.g., varices present = “No” will be chosen over varices present = “Yes”, varices grade = “Unknown” will be chosen over varices grade = “Small”), and the more severe record will be selected for postbaseline visits.

Data that are continuous in nature but are less than the lower limit of quantitation (LOQ) or above the upper LOQ will be imputed as follows:

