6.4.2. Liver Imaging, Biopsy, Endoscopy and Transplant

Imaging of the liver will be performed as part of standard of care (e.g., CT, MRI, or Ultrasound results, if available). Liver biopsy will be performed at any time only if results available from biopsy performed as part of standard of care. An endoscopy will be performed to evaluate for varices at any time or at Day 1 (+/- 6 months) and within 6 months prior to Week 240 visit as in protocol. Liver transplant will be reported during the study.

A shift table of varices grade from endoscopy (no varices/small varices/large varices/unknown) from Day 1 to Week 240 will be provided by treatment group and baseline CTP class (CTP A, B, C, Unknown and total).

The results of all above will be listed by participant ID number and study visit. Results of endoscopy/imaging/biopsy collected at Day 1 visit but with a procedure date before or on the most recent HCV treatment end date will be flagged in the listing.

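### For a Day 1 endoscopy reported more than once, SAP 3.7 lets an unknown varices grade replace a known one; it also leaves open whether repeated HCC dates are imputed before the earliest is chosen

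*SAP*

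**What the plan says.** **Varices.** SAP 3.7 has a rule for a single test that appears in the data several times: "For an endoscopy/liver imaging test conducted on one day but repeatedly reported in multiple visits". If the reports disagree, "The milder record will be selected for baseline if there are different reported test results", while "the more severe record will be selected for postbaseline visits". One of its baseline examples is "varices grade = “Unknown” will be chosen over varices grade = “Small". The grade feeds SAP 6.4.2, which plans "A shift table of varices grade from endoscopy (no varices/small varices/large varices/unknown) from Day 1 to Week 240", by treatment group and by baseline CTP class. The same section lists all endoscopy results by participant and visit.

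Elsewhere the SAP works with non-missing data. Section 3.8.1 takes baseline from non-missing values, and section 3.8.3 chooses among valid non-missing measurements unless a different rule is specified.

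**HCC dates.** For follow-up and time-to-event calculations, SAP 3.7 says that "partial dates will be imputed as 01 if only day is missing, as 01 January if day and month are missing". A separate paragraph says: "For an HCC event that is reported in multiple visits, the earliest diagnosis date is used as the first HCC event occurrence date". There is a check on implausible imputed dates for death, but none for HCC. The text does not say whether imputation comes before or after selection of the earliest date.

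**The concern.** Unknown is not a degree of severity; it means that the grade is missing. Taking the milder result at baseline is a defensible convention when two reports truly disagree, such as Small against Large. It gives no reason to let a report without a grade displace a report of the same procedure that has one. Nothing is in conflict in that case, because one report is simply less complete.

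What is at stake is the readability of the shift table. Protocol 6.3.6 schedules endoscopy only at Day 1 and around Week 240, so a lost Day 1 grade is not replaced by another scheduled examination. Protocol 8.6.2 counts varices among the clinical signs of progression or regression.

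The HCC dates raise a similar question. Partial dates are set to the earliest possible day and the earliest date is then preferred, so a vaguer report could override an exact one. The HCC date enters the Kaplan-Meier analysis of a primary endpoint (SAP 6.1.3.2.1).

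**Working it through.** The plan gives no figure to reproduce on this point.

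**Step 1: apply the varices rule to one endoscopy reported once as Unknown and once as Small.**

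| Window | Rule in SAP 3.7 | Value used |
|---|---|---|
| Baseline | milder report | Unknown |
| Postbaseline | more severe report | Small |

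The baseline result is the SAP's own example. The postbaseline result follows from the same ranking. The loss therefore arises at baseline only. If Unknown ranks below Small, it also ranks below Large, so a known Large at Day 1 would be displaced as well.

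**Step 2: read the shift table for a participant whose Day 1 grade is in truth Small.**

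| Week 240 grade | Day 1 = Small | Day 1 = Unknown |
|---|---|---|
| None | regression | regression, if Unknown means present but ungraded |
| Small | no change | unreadable: no change, or regression from Large |
| Large | progression | unreadable: no change, or progression from Small |

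The SAP does not define Unknown. If it can also mean that presence itself is not known, the first row becomes unreadable too.

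**Step 3: HCC dates, if imputation comes first.** Assume that the exact date is uniform over the calendar, and that a second report of the same HCC gives only its month and year, or only its year. The imputed date is then never later than the exact date.

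- Day missing, 365-day year: mean shift = [7 × (31×30/2) + 4 × (30×29/2) + 28×27/2] / 365 = (3255 + 1740 + 378) / 365 = 14.7 days, with a maximum of 30.
- Day and month missing: mean shift = (0 + 364) / 2 = 182 days. This is 182/168 = 1.08 of the 24-week intervals in the Kaplan-Meier table.
- Running through every date in 2015 to 2021 (an assumed span) gives means of 14.7 and 182 days. The imputed date is strictly earlier for 96.7% of dates when the day is missing, and for 99.7% when day and month are missing.

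Example with assumed dates: registry start on 10 June 2016 and exact HCC date 15 September 2016 give day 97 + 1 = 98. A second report of September 2016 gives day 83 + 1 = 84.

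**Step 4: HCC dates, if selection comes first.** If the earliest date is picked among reports as entered, and imputed only if the chosen one is partial, an exact date may survive. The SAP does not say how a partial date would then be ranked against an exact date in the same month or year.

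**The case against.** The best defence is one of scope. The varices rule needs one procedure, reported more than once with differing results, in the baseline window. It affects one descriptive table under Other Measurements. The progression events in SAP 6.1.3.2.1 include bleeding varices, not varices grade, and no hypothesis is tested. Milder at baseline and worse afterwards is a deliberate convention that matches the handling of same-day categorical records in SAP 3.8.3. Discrepancies are queried (Protocol 9.1.6) and resolved or adjudicated before the final analysis (SAP 2.2). All of this stands and limits the weight of the point. None of it justifies placing a missing grade inside the severity order.

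Several stronger readings are tempting, and the documents do not support them:

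- *Known grades are discarded altogether.* They are not, because the results stay in the listings.
- *A participant in the unknown row can show neither progression nor regression.* Step 2 shows that a move to no varices could still be read as regression if Unknown means present but ungraded.
- *The SAP prefers an imputed HCC date to an exact one.* It does not say so, because the order of the two steps is unstated. Liver events are asked about since the last visit, with visits 24 weeks apart (Protocol 6.3.5 and 3.1), so a year-only repeat of an exactly dated HCC should be unusual.
- *Any shift above 168 days must change a table column.* The last column spans 1710 − 1512 = 198 days. An event moved from day 1700 to day 1530 shifts by 170 days and stays in it.
- *De novo HCC cases would be reclassified as prior HCC.* In the Step 3 example, a year-only repeat gives 1 January 2016, which is 161 days before registry start. But SAP 6.1.3.2.1 rests prior status on HCC having been identified before registry start, and does not say that an imputed date decides this.

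**Conclusion.** The varices point holds as written in the SAP. At baseline, a missing grade displaces a known one from the same endoscopy, and a later small or large grade then cannot be interpreted in the shift table. The effect is confined to that summary. The documents give no frequency, so no count can be stated. As a scale only, 2% to 10% of an assumed 200 participants with small varices at Day 1 would be 4 to 20, and neither input comes from the documents.

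The HCC point is secondary and conditional. The order of imputation and selection is not stated, and no rule protects an exact date that is compatible with a partial one. If imputation comes first, the mean shift is about 15 days with the day missing and about 182 days with day and month missing, for uniformly distributed dates and a second report from the same month or year.

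**What to change.** In SAP 3.7:

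1. **Varices.** Treat Unknown as missing whenever another report of the same endoscopy gives a grade. Apply the milder (baseline) or more severe (postbaseline) order only among known results.
2. **HCC dates.** If a partial date is compatible with a complete date for the same HCC (same month and year, or same year when the month is missing), use the complete date. Otherwise keep the earliest-date rule, and impute only when no compatible complete date exists.

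The compatibility condition matters. If one report gives November 2015 and another gives 10 February 2016, the partial date is certainly earlier, and a blanket preference for complete dates would wrongly drop it.

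The cost is two short wording changes and a small edit to the derivation code, with no new data. SAP section 1 already provides for changes after finalization to be documented in the CSR.

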3.8. Visit Windows

3.8.1. Definition of Visits

Baseline Value will be the first non-missing value taken on or within 30 days of the registry start date (i.e., Day 1 Visit of the registry collected from the demographic eCRF). For questionnaire data, if no data are available within 30 days after the registry start date, the baseline value will be the last non-missing value prior to the registry start date.

Study days are calculated relative to registry start date as follows:

- For measurements that are collected before the registry start date: Visit date – registry start date.
- For measurement or events that are collected on or after the registry start date: Visit date – registry start date +1.

Last Day of the registry is the last recorded non-missing visit or collected data/assessment date in the database. When determining the last day of the registry, partial date will be imputed as 01 if only day is missing and 01 January if day and month are missing.

3.8.2. Analysis Windows

Participant visits might not occur on protocol-specified visit days. Therefore, for the purpose of analysis, observations (corresponding laboratory test or quality of life questionnaires) will be assigned to analysis windows. Windows will be constructed so that the boundaries of windows are the midpoint between consecutive protocol-specified visit days. The analysis windows for liver disease assessment, laboratory data, Model for End-Stage Liver Disease (MELD) score and data from quality of life survey Short Form-36 (SF-36) are defined in [Table 3-1](#). The analysis windows for transient elastography (Fibroscan score) are defined in [Table 3-2](#). Endoscopy will be assigned to either Day 1 or Week 240 with +/- 6 months based on the test performed date as shown in [Table 3-3](#).

Table 3-1. Analysis Windows for Liver Disease Assessment, Laboratory Data, CTP/MELD Score and Quality of Life Surveys

Analysis Visit ID	Nominal Day	Lower Limit	Upper Limit
Baseline ^a	1	1	30
Baseline ^b	1	(none)	30
Week 24	168	31	252
Week 48	336	253	420
Week 72	504	421	588
Week 96	672	589	756
Week 120	840	757	924
Week 144	1008	925	1092
Week 168	1176	1093	1260
Week 192	1344	1261	1428
Week 216	1512	1429	1596
Week 240	1680	1597	>=1680

a Baseline window for laboratory tests, liver disease assessment and CTP/MELD score only.

b Baseline window for Quality of Life Surveys only.

Table 3-2. Analysis Windows for Transient Elastography (Fibroscan Score)

Analysis Visit ID	Nominal Day	Lower Limit	Upper Limit
Baseline	1	-75	168
Week 48	336	169	504
Week 96	672	505	840
Week 144	1008	841	1176
Week 192	1344	1177	1512
Week 240	1680	1513	>=1680

Table 3-3. Analysis Windows for Endoscopy

Analysis Visit ID	Nominal Day	Lower Limit	Upper Limit
Day 1	1	-182 (about -6 months)	182 (about 6 months)
Week 240	1680	1513 (about 6 months prior/Week 216)	>=1680
Others*	-	-	-

* For endoscopy performed to evaluate for varices at time other than the two protocol-defined visits, the test result will be assigned to the closest protocol scheduled liver disease assessment visit.

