### **6.2.1. Weeks 24, 72, 120, 168, and 216 (+/- 4 weeks)**

Subjects will be asked to come in fasting for these visits. The following procedures will be performed and documented:

- Complete Health Related Quality of Life (HRQoL) surveys
- Conduct limited physical exam
- Collect information for liver disease assessment
- Obtain blood samples (For subjects enrolling from the GS-US-248-0122 study, blood samples do not need to be collected for both studies if the ET from GS-US-248-0122 and D 1 visit from GS-US-337-1431 are done on the same day)
- Record any serious adverse events or adverse events that are related to protocol-required procedures

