### 6.3.6. Endoscopy

An endoscopy will be performed to evaluate for varices at Day 1 (+/- 6 months) and within 6 months prior to Week 240. There is no need to repeat if subject has available endoscopy results performed within 6 months prior to Day 1 or Week 240 as part of standard of care. The results of the endoscopy will be recorded into the clinical database.

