6.1.3. Primary Analysis of the Primary Endpoints

6.1.3.1. Proportion of Participants Maintaining SVR Through Week 240

Definition of Virologic Failure: Virologic failure is defined as having 2 consecutive blood samples (at least one week apart) with HCV RNA > LLOQ, or last available HCV RNA > LLOQ with no subsequent follow-up values. Date of virologic failure is the date of the first measurement if confirmed by 2 consecutive measurements, or the date of the last available HCV RNA > LLOQ with no subsequent follow-up values.

Participants who early terminated the study by a visit for a reason other than virologic failure are censored for that visit. In addition, participants who completed the study without a virologic failure are censored at the end of study by standard Kaplan-Meier (KM) methods.

Person-time pertaining to KM analysis of time to virologic failure will be calculated as: date of virologic failure (for participants who experienced virologic failure) or last day of registry (for participants who did not experience virologic failure) – registry start date + 1.

SVR end date will be the date to have HCV RNA level that was measurable during the registry study.

The KM estimate of the proportions of participants who maintained SVR, and the cumulative number of participants who experienced virologic failure, were at risk, and had been censored will be summarized by treatment group and by time point (Week 0, 24, 48, ..., 216 and 240), where Week 0 to 216 are the exact weeks elapsed since registry start date (i.e. 0, 168, 336, ..., and 1512 days), and Week 240 includes 1680 days elapsed since registry start date plus additional 30 days (i.e. 1710 days). The KM plots will also be presented in a figure.

A by-participant, by-visit listing of the actual HCV RNA value and \log_{10} HCV RNA will be provided by participant ID number in ascending order. A separate by-participant, by-visit listing of the actual HCV RNA value and \log_{10} HCV RNA will be provided for participants with virologic failure by participant ID number in ascending order, including time since registry start date to virologic failure, and time since the end of the most recent HCV treatment to virologic failure, parent study ID, most recent HCV treatment, and baseline CTP category.

Participants who experienced virologic failure more than 30 days after 240 weeks elapsed since registry start date (i.e. > 1710 days) will be listed separately.

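### SAP Table 3-3 counts 6 months as 182 days at Day 1 but as 167 days at Week 240, so some protocol-compliant final endoscopies miss the varices shift table

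*SAP*

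**What the plan says.** Protocol section 6.3.6 sets the timing: "An endoscopy will be performed to evaluate for varices at Day 1 (+/- 6 months) and within 6 months prior to Week 240". It accepts a standard-of-care endoscopy from the same period without a repeat, and section 6.2.3 says the same for the Week 240 visit.

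SAP section 3.8.2 gives the analysis rule: "Endoscopy will be assigned to either Day 1 or Week 240 with +/- 6 months based on the test performed date". Table 3-3 turns this into days:

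- The Day 1 row runs from minus "182 (about -6 months") to plus 182.
- The Week 240 row has nominal day 1680 and opens at Day "1513 (about 6 months prior/Week 216").
- Any other endoscopy goes to the nearest scheduled liver disease assessment visit.

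SAP section 6.4.2 restates the protocol's timing. It also plans the output that uses these windows, a shift table of varices grade "from Day 1 to Week 240 will be provided by treatment group and baseline CTP class". SAP section 6.5 declares no departure from the protocol's endpoint analyses.

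**The concern.** Two adjacent rows of one table carry the label of about 6 months but use different lengths, and the shorter one applies to the final endoscopy. Windows are applied by the date of the test, so reporting the result at the Week 240 visit does not bring an earlier test into the Week 240 row. A participant whose final endoscopy fell just before Day 1513 followed the protocol, had no reason to repeat the test, and still has no Week 240 value from it.

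What is at stake is the completeness of the paired varices data. Protocol section 8.6.2 lists varices among the signs of progression or regression, and the synopsis schedules only two endoscopies per participant. When the final one is assigned elsewhere, there may be no other to fill the Week 240 cell.

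**Working it through.** **Inputs.**
- Week 240 lower limit: Day 1513 (SAP Table 3-3).
- Nominal Week 240: Day 1680 (Table 3-3; SAP section 6.1.3.1 also has "Week 240 includes 1680 days elapsed since registry start date").
- 6 months in days: 182 (Day 1 row of Table 3-3).
- Week 240 visit tolerance: 4 weeks either side, so Days 1652 to 1708 (protocol section 6.2.3).
- Study day on or after registry start: elapsed days plus 1 (SAP section 3.8.1).

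**Can 1513 be reproduced as 6 months before Week 240?** The length used is 1680 − 1513 = 167 days, about 5.5 months. The usual conversions give:

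| 6 months taken as | Lower limit (1680 − length) | Days short (1513 − limit) |
|---|---|---|
| 180 days | 1500 | 13 |
| 182 days (the SAP's own) | 1498 | 15 |
| 183 days | 1497 | 16 |

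None gives 1513. Counting back 182 days from study day 1681 (an exactly on-time visit under the plus-1 rule) gives 1499, which is 14 days short.

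Day 1513 does reproduce as Week 216: 24 weeks is 168 days, and 1681 − 168 = 1513. It also equals the Week 240 lower limit for elastography in Table 3-2, (1344 + 1680)/2 + 1 = 1513.

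**Where do the affected tests go?** Days 1498 to 1512 are 15 days. The nearest scheduled visit is Week 216 (nominal Day 1512), so the residual rule sends them there. The shift table uses Day 1 and Week 240 only.

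**How does the shortfall depend on the actual Week 240 visit?** For a visit on day V, the compliant period starts at V − 182, and the excluded compliant days number max(0, 1513 − (V − 182)).

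| Week 240 visit | Compliant from | Compliant days excluded |
|---|---|---|
| Day 1652 (4 weeks early) | 1470 | 43 |
| Day 1680 (nominal) | 1498 | 15 |
| Day 1695 | 1513 | 0 |
| Day 1708 (4 weeks late) | 1526 | 0 |

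**Share affected.** If final endoscopies were spread evenly over Days 1498 to 1680 (183 days, an assumption), the share is 15/183 = 8.2%.

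**The case against.** The strongest defence is that the cell discloses both an approximation and an anchor. It says about 6 months and names Week 216, and 24 weeks before an on-time Week 240 visit is exactly study day 1513. The SAP itself treats 240 weeks as roughly 5 years, and on that scale 24 weeks is half a year. This part stands: the entry is best read as a second convention for 6 months, not as a slip in subtraction. It does not remove the conflict, because the row above applies the same label as 182 days and the protocol's limit is 6 months.

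The effect is also small. The results are reassigned and not deleted, and SAP section 6.4.2 lists every endoscopy. One descriptive table under other measurements is touched, and no hypothesis is tested. Bleeding varices, the variceal event in the time-to-event analysis, come from the liver disease assessment page and are unaffected.

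A reader might infer a much larger loss from the schedule tables, which as extracted mark the second endoscopy under Week 216. Protocol section 6.2.1, "Weeks 24, 72, 120, 168, and 216 (+/- 4 weeks"), allows that visit on Days 1484 to 1540, and 29 of those 57 days (51%) fall before Day 1513. The documents do not support a claim that about half of final endoscopies are lost:

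- Section 6.2.1 lists no endoscopy, the synopsis places the test at Day 1 and Week 240, and the mark may be a merged cell.
- Days 1484 to 1497 lie within 182 days of Week 240 only if that visit is also early. Against nominal Week 240, the compliant part of the Week 216 window is Days 1498 to 1540, and 15 of those 43 days (35%) are excluded.
- Nothing shows that any site did the test at Week 216.

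**Conclusion.** The inconsistency holds. The Week 240 window is 15 days shorter than the 182-day convention in the same table, and it conflicts with the SAP text and with the protocol's 6-month allowance. Depending on the actual Week 240 date, between 0 and 43 days of compliant testing fall outside it.

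The 8% figure rests on the even-spread assumption and on a Week 240 visit at its nominal day. The number of participants affected cannot be derived from the documents. The consequence is limited to missing Week 240 entries in one descriptive shift table. A reader might go further and say that data are discarded or that a primary time-to-event result is biased; the listing rule and the source of the variceal events rule out both. This is a consistency correction worth making because it costs almost nothing.

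**What to change.** In SAP Table 3-3, set the Week 240 lower limit to Day 1498 (1680 − 182). Where a Week 240 visit took place, the limit can instead be the earlier of Day 1498 and the actual visit date minus 182 days. Keep the rule in SAP section 3.8.3 that selects the record closest to the nominal day.

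Two simpler alternatives are worse:

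- Visit date minus 182 days on its own would open at Day 1526 for a visit on Day 1708. That drops Days 1513 to 1525, which the SAP now includes, and it is undefined when there was no Week 240 visit.
- A fixed Day 1484 would cover the whole Week 216 visit window but lies 196 days (28 weeks) before nominal Week 240, beyond 6 months.

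The change is to one table entry, with a footnote if the visit-based option is used. It needs no new data and does not alter when endoscopies are done. The downside is that a few slightly earlier endoscopies count as Week 240. If the sponsor prefers to keep Day 1513, the SAP should say that 24 weeks is intended, reconcile this with its own text and the Day 1 row, and report how many final endoscopies fall on Days 1498 to 1512.
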